#### 6.4.2.2 Monitoring for EBV reactivation

EBV seronegative patients who have received organs from EBV seropositive donors are excluded from participation to decrease the risk of developing PTLD. In addition, evidence of EBV replication will be assessed using PCR testing throughout the period of study drug administration.

6.5 Non-therapy Precautions and Restrictions6.5.1 PrecautionsNone.

6.6 Withdrawal of Subjects from Study

All efforts should be made to follow all subjects for the entire duration of the study. Withdrawal of a subject from study medication (Section 6.2.4) does not imply that the subject is withdrawn from the study. Section 7.2.4 details study-related procedures for subjects who discontinue study medication.

Subjects MUST be discontinued from study therapy AND withdrawn from the study for the following reasons:

• Withdrawal of informed consent (subject's decision to withdraw for any reason)

• Any clinical AE, laboratory abnormality, or intercurrent illness which, in the opinion of the investigator, indicates that continued treatment with study therapy and further participation in the study (including obtaining vital status of the subject and allograft) is not in the best interest of the subject

• Termination of the study

• Subjects who become prisoners or become involuntary incarcerated for treatment of either a psychiatric or physical (e.g., infectious disease) illness. For discontinuation of study therapy, see Section 6.2.4.

22

#### 6.6.1 Discontinued Subjects

The investigator should accept only those subjects who give a reasonable indication that they will complete the study. An evaluation that reflects the status of the subject at premature termination, with a final assessment and reasons for termination, must be provided by the investigator.

See Section 7.2.4 for a list of the procedures to be completed for subjects who discontinue study medication.

7 STUDY PROCEDURES AND OBSERVATION 7.1 Time and Events Schedule

See figure 2 below and Table for outline of events.

Large arrow indicates 12 months of study duration. Study visits indicated by small arrows, study-provided belatacept administration by asterisks. Grey line indicates interruption in scale between 6 month and 12 month time point. Extension from 6 to 12 months of therapy is optional.

	Baseline	Day	Week	Week	Week	Week	Week	Week	Week	Week	Week
Obtain informed consent	X	1	2	4	0	0	12	10	20	24	40#
Confirm inclusion/exclusion criteria	Х										
Full medical history	X										
Physical exam	Х						Х			Х	
Weight/Vital signs	Х	Х	Х	Х	Х	Х	Х			Х	
Drug infusion*		Х	Xa	X b	Xb	Xc					
Donor specific Ab testing	Х			Х			Х			Х	Х
Study labs	Х			Х			Х			Х	Х
Pregnancy test**	Х						Х			Х	Х
Review concomitant medications	Х	Х	Х	Х	Х	Х	Х			Х	Х
AE monitoring	Х	Х	Х	Х	Х	Х	Х	Х	Х	Х	Х
Local laboratory testing**	Х	Х	Х	Х	Х	Х	Х	Х	Х	Х	Х
EBV PCR testing	Х			Х			Х			Х	Х

Table: Study Procedures

\*Belatacept will be administered at 5mg/kg

\*\*If applicable

\*\*\* Standard of care laboratory testing will be performed at each visit following standard care practices at our center

#For patients who elect to continue additional 6 months of belatacept therapy

 $^{\rm a}$  +/- 2 days

 $^{b}$ +/- 3 days

c+/- 7 days for patients who elect to continue additional 6 months of belatacept therapy

#### 7.2 Procedures by Visit

Study procedures for the screening, baseline, and post-belatacept administration period are detailed in chart form in the table above and described further below.:

#### 7.2.1 Screening/Baseline Evaluations

a) Screening may occur at any time for subjects 0 to 3 months after kidney transplantation who may meet study criteria

b) If patients appear to be possible candidates for enrollment, obtain written informed consent and enroll the subject. Consent must be obtained prior to any change in medical therapy or any procedure performed solely for the purpose of this study (A subject is considered enrolled in the study upon signing informed consent. Some standard-of-care

procedures routinely obtained for transplant subjects, regardless of study involvement, are likely to be obtained prior to study participation consent date, and should be documented as such.)

- c) Assign a unique study number to the patient
- d) Obtain complete medical history and physical examination.

e) Obtain body weight (clothes on, shoes off), and measure vital signs (blood pressure (BP), heart rate, temperature, and respiration).

f) Study labs will be drawn by obtaining whole blood and sending it via courier to the Immunogenetics Center for separation into PBMC and serum and storage. PCR testing will be performed.

g) DSA testing

h) Check and record all concomitant medications

7.2.2 Day 1

a) Confirm all inclusion/exclusion criteria.

b) Obtain height and body weight (clothes on, shoes off), and measure pre-dose vital signs (BP, heart rate, temperature and respiration). Height and weight recorded for Day 1 can be obtained 1 day prior, if necessary.

c) Assess and record AEs pretreatment.

d) Check and record any changes in concomitant medications.

e) Ensure all pretreatment (baseline) laboratory assessments and procedures have previously been obtained, or obtain at Day 1 prior to start of any study dosing (i.e., a negative serum pregnancy test must be confirmed within 72 hours of initiation of study dosing, if previous test is not within 72 hours, repeat prior to dosing at Day 1). Draw baseline whole blood for immunology analysis if not previously drawn

f) Administer study medication (belatacept 5 mg/kg over 30 minutes i.v. )

g) Continue daily dosing of prednisone, MMF, doses to be determined by the subject's treating physician, to continue throughout the duration of the study following practices of standard medical care

7.2.3 Infusion-only Visit Procedures

a) To occur on Days 1 as above, as well as weeks 2, 6, 8, 16, and 20

- b) Obtain weight and vital signs
- c) Review for changes in concomitant medication and AEs
- d) Administer study medication

#### 7.2.4 Standard Study Visits

a) To occur on Weeks 4, 12, and 24 as well as week 48 for those electing to continue in the study

- b) Assess and record AEs pretreatment.
- c) Check and record any changes in concomitant medications
- d) Obtain weight and vital signs

e) Draw whole blood for immunology analysis, to be sent by courier to the Immunogenetics Center

- f) DSA testing
- g) EBV PCR testing

### h) WOCBP will undergo pregnancy testing at weeks 12 and 24 as well as week 48 for those continuing in the study

i) Administer study medication

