#### 1.3 Rationale for Dosing

Based on the IM 103-116 study of conversion from CNI to belatacept for maintenance of immunosuppression in kidney transplant recipients, a similar dosing schedule will be used with belatacept 5mg/kg every two weeks for a total of 5 doses followed by monthly administration of belatacept at the 5mg/kg dose.

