#### Age and Gender

4) Men and women, ages 18 and older, inclusive

5) Women of childbearing potential (WOCBP) must be using an adequate method of contraception to avoid pregnancy throughout the study and for up to 8 weeks after the study in such a manner that the risk of pregnancy is minimized. See section 9.7 below for details regarding handling of WOCBP subjects.

WOCBP includes any female who has experienced menarche and who has not undergone successful surgical sterilization (hysterectomy, bilateral tubal ligation, or bilateral oophorectomy) or is not postmenopausal (defined as amenorrhea  $\geq 12$  consecutive months; or women on hormone replacement therapy with documented serum follicle stimulating hormone level > 35 mIU/mL). Even women who are using oral, implanted, or injectable contraceptive hormones or mechanical products such as an intrauterine device or barrier methods (diaphragm, condoms, spermicides) to prevent pregnancy or practicing abstinence or where the partner is sterile (e.g., vasectomy), should be considered to be of child bearing potential. WOCBP who are taking MMF must in addition use methods of birth control as stipulated in the package insert, namely:

Either intrauterine device, or partner with vasectomy, or one hormone (oral contraceptive pill, transdermal patch, vaginal ring, or progesterone injection or implant) and one barrier method (diaphragm or cervical cap with spermicide, contraceptive sponge, or male or female condom), or two barrier methods as described above.

WOCBP must have a negative serum pregnancy test (minimum sensitivity 25 IU/L or equivalent units of human chorionic gonadotropin [HCG]) within 72 hours prior to the start of study medication then every 3 months during the period of study participation.

6) Men must use an adequate method of contraception throughout the study, and for up to 8 weeks after the last infusion, so that the risk of pregnancy to their partners is minimized.

7) MMF must be dosed at 500 mg by mouth twice daily or greater at the time of study entry

8) Prednisone must be dosed at >=10 mg by mouth daily for patients less than 6 weeks posttransplantation, and at >=5mg by mouth daily for patients greater than 6 weeks posttransplantation at the time of study entry.

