#### Belatacept Regimen

Subjects will receive intravenous belatacept at 5mg/kg every other week starting from day 1 and continuing with weeks 2, 4, 6, and 8, and then monthly at months 3, 4, 5, and 6. At month 6 patients may elect to continue for an additional six-month period of belatacept administration.

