#### Pregnancy Tests:

A serum pregnancy test (minimum sensitivity 25 IU/L of ß-HCG) must be performed at a local laboratory for all WOCBP within 72 hours prior to the first dose of study medication (baseline or Day 1). Additional testing will occur at weeks 12 and 24, and week 48 for those continuing in the study.

If a female subject becomes pregnant, she will be discontinued from the study.

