#### Timing of Pregnancy Testing

*Outpatient Trials*: WOCBP should be tested:

• At screening

- Every 3 months during period of study participation
- Whenever pregnancy is suspected

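### The visit schedule has no pregnancy test between weeks 24 and 48 of the optional extension, although sections 5.1 and 9.7 require one every 3 months

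*Combined protocol and SAP*

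**What the plan says.** The frequency rule appears twice. Section 5.1 (Age and Gender) requires a negative serum test "within 72 hours prior to the start of study medication then every 3 months during the period of study participation". Section 9.7 (Timing of Pregnancy Testing) repeats the interval: "Every 3 months during period of study participation". Neither limits the rule to the first 6 months.

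The extension is part of the study. Section 3.1.1 gives a 6-month duration that may be extended by 6 months, and section 6.2.2 says "At month 6 patients may elect to continue for an additional six-month period of belatacept administration".

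The dates for testing are fixed elsewhere. Section 7.2.4 item h says "WOCBP will undergo pregnancy testing at weeks 12 and 24 as well as week 48 for those continuing in the study". Section 7.3.4, after the pre-dose test, says "Additional testing will occur at weeks 12 and 24, and week 48 for those continuing in the study". The procedures table in section 7.1 marks the test at baseline, week 12, week 24 and one column for extending subjects.

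No visit that could carry a further test is listed. Standard visits are "To occur on Weeks 4, 12, and 24 as well as week 48 for those electing to continue in the study", and infusion-only visits are "To occur on Days 1 as above, as well as weeks 2, 6, 8, 16, and 20".

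**The concern.** The two sets of text cannot both be followed during the extension. Staff who work from the visit list and table will test at weeks 24 and 48 and breach sections 5.1 and 9.7. Staff who work from those sections will test near week 36, at a visit the schedule does not name.

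What is at stake is how soon a pregnancy is found during treatment. Every subject takes MMF (section 6.2.6.2), and section 7.3.2 notes its hazard to the fetus. Sections 6.2.4 and 7.3.2 require study medication to stop at once when a subject becomes pregnant. Section 9.7 allows continued treatment only with IRB approval and requires the sponsor to be notified within 24 hours. For MMF, section 7.3.2 calls for registry reporting and a discussion of risk and benefit. Each of these steps depends on detection. An unsuspected pregnancy that begins soon after week 24 would have no scheduled test for nearly 24 weeks.

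**Working it through.** The plan gives no figure to reproduce, so the check compares the required interval with the scheduled dates.

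**Inputs**
- Required interval: 3 months (5.1, 9.7).
- Scheduled tests: baseline (week 0) and weeks 12, 24 and 48 (7.2.4 h, 7.3.4, table in 7.1). The table's extension column is read as week 48, to agree with the two text sections.
- Visit windows (7.2.6): ±3 days from week 4 to month 6, and ±7 days at month 12.
- Maintenance dosing: "followed by monthly administration of belatacept at the 5mg/kg dose" (1.3), with months 4 and 5 run as weeks 16 and 20 (7.2.3).

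**Interval in weeks**

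3 months = 365.25 / 4 / 7 = 13.04 weeks (91.3 days).

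**Gaps on nominal dates**

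| From | To | Gap (weeks) | Gap / 13.04 | Meets the rule |
|---|---|---|---|---|
| 0 | 12 | 12 | 0.92 | yes |
| 12 | 24 | 12 | 0.92 | yes |
| 24 | 48 | 24 | 1.84 | no |

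**Could the windows explain it?**
- Shortest last gap: 168 − 3 − 7 = 158 days; 158 / 91.3 = 1.73.
- Longest last gap: 168 + 3 + 7 = 178 days; 178 / 91.3 = 1.95.

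The gap is well over 3 months at either end. If the table's last column were read as week 40, the gap would be 40 − 24 = 16 weeks, and 16 / 13.04 = 1.23, which still exceeds the rule.

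**Infusions covered by each test**

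The protocol does not list extension infusion dates. This count assumes that the 4-weekly pattern of weeks 16 and 20 continues.
- Week 12 test: infusions at weeks 12, 16 and 20, so 3.
- Week 24 test: infusions at weeks 24, 28, 32, 36, 40 and 44, so 6.

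**With a week 36 test added**
- Gaps become 12, 12, 12 and 12 weeks, all below 13.04.
- On the same dosing assumption, the week 24 test covers weeks 24, 28 and 32 (3 infusions), and the week 36 test covers weeks 36, 40 and 44 (3 infusions).
- If week 36 had a ±3-day window, the longest gap to month 12 would be 84 + 3 + 7 = 94 days (13.4 weeks), slightly over 91.3. The new test therefore complies on nominal dates but needs attention to its window.

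**The case against.** The strongest reply is that the binding rule is already in the protocol, twice, so the fault is an incomplete visit list and a careful site would test near week 36 anyway. Other safeguards exist. Contraception is mandatory, with methods specific to MMF (5.1). Women unwilling or unable to use it are excluded (5.2). Subjects are told to contact the investigator at once about a missed or late period, and a test follows any suspicion (9.7). Section 9.7 warns that drug interactions may weaken hormonal contraceptives, but it also restricts their use, and section 5.1 requires a barrier method alongside a hormone. The group concerned is small and optional, and no endpoint is involved.

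Much of this stands, and it bears on how much harm to expect. It does not remove the conflict. Section 7.3.4 states when further testing takes place and leaves out week 36, so following it literally breaks the rule. Testing on suspicion cannot find an unsuspected pregnancy, and the protocol requires routine testing in addition to contraception.

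Two narrower points also stand. The infusion count rests on an assumed extension schedule; the 24-week gap does not. Because no week 36 visit is defined, the correction must name the visit and its window as well as the test.

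**Conclusion.** The concern holds. The schedule omits one pregnancy test that the protocol's own rule requires for each woman of childbearing potential who continues past month 6. The gap is 24 weeks against about 13, or 1.84 times the interval on nominal dates and 1.73 to 1.95 times across the visit windows. The first 6 months comply.

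This rests on reading the 3-month rule as applying throughout participation, as its wording says, and on counting the extension as participation. The number affected is not given: it is the women of childbearing potential among 0 to 20 extending subjects, and could be zero. This is a safety-schedule fault that should be corrected. It has no bearing on sample size, the month 6 comparisons or the analysis.

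**What to change.** Add a week 36 pregnancy test for women of childbearing potential who continue in the study to section 7.2.4 item h, section 7.3.4 and the procedures table. Draw it before the infusion at that visit. The table needs a week 36 column, and section 7.2.6 needs a window for it. To keep the last gap within 3 months whatever the windows, state that the week 48 test falls no more than 13 weeks after the week 36 test. Listing the extension infusion visits in section 7.2.3 would give the test a defined visit.

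The cost is a short edit in each place and one test per extending woman of childbearing potential, at most 20 × 1 = 20 tests. No extra attendance is needed if the test is drawn at a monthly infusion.

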#### 7.2.5 Early Termination Procedures

For randomized, transplanted, and treated subjects who received at least 1 dose of study medication and discontinue from study medication for any reason, if informed consent continues to be provided we will continue to perform study procedures scheduled for weeks 4, 12, and 24 including an additional study lab draw at the time of drug discontinuation if it is not within 14-days of one of the above listed study visits

#### 7.2.6 Visit Windows

To facilitate scheduling the infusion-only visits, the following windows are permitted for subsequent doses:

Visit Visit Window

Week 2	Target date ± 2 days
Week 4 - Month 6	Target date ± 3 days
Month 12	Target date ± 7 days

#### 7.3 Details of Procedures

All assessments should be performed or administered prior to study drug administration unless otherwise indicated.

7.3.1 Study Materials Local laboratory will be used for all testing

#### 7.3.2 Safety Assessments

Safety assessments include AEs, clinically significant changes in vital signs, physical examination, and laboratory test abnormalities. The investigator will determine the severity of each AE as mild, moderate, severe, or very severe. In addition, the investigator will determine the relationship of the AE to the administration of the study drug.

Physical examinations may be performed by a Doctor of Medicine, Doctor of Osteopathy, Physician's Assistant, or Nurse Practitioner.

Urine or serum pregnancy tests will be performed prior to the first dose for all WOCBP. If any female subject becomes pregnant, she will be immediately discontinued from study medication.

In addition, for women who become pregnant while using MMF or within 6 weeks of discontinuing therapy, study personnel or the patient's healthcare practitioner will report the pregnancy to the Mycophenolate Pregnancy Reference Registry ([name]) and will strongly encourage the patient to enroll in the pregnancy registry. The patient will also be apprised of the potential hazard of mycophenolate products to the fetus. The risks and benefits of MMF will be discussed with the patient. In certain situations, the patient and her healthcare practitioner may decide that the maternal benefits outweigh the risks to the fetus.

#### 7.3.2.1 Events of Special Interest

• Subject death or graft loss (Confirmation of graft loss by a SCr criterion [see Section 3.3 for definition] requires determination of central SCr  $\ge$  6 mg/dL for  $\ge$  4 weeks. Therefore, an additional central laboratory test(s) may be required.)

- Acute rejection
- PTLD
- Infections
- 7.3.3 Other Assessments

#### 7.3.3.1 Kidney Allograft Biopsy

Allograft biopsies are to be performed as determined by the patient's treating physician following standard practice at the study institution. The Banff 97 working classification of kidney transplant pathology will be used for grading of rejection.

#### 7.3.4 Laboratory Test Assessments

Study labs for immunologic monitoring should be obtained prior to infusions. In addition, standard lab testing will be performed as part of the patient's ongoing clinical care under the direction of their treating physician. Laboratory personnel will be blinded to the patient's demographic characteristics and clinical status. Any laboratory test result that the investigator considers clinically relevant will be recorded as an AE.

List of tests:

Immunology testing:

Whole blood will be collected at baseline and at Weeks 4, 12, and 24. Samples must be taken prior to beginning the infusion of belatacept. Additionally, a sample for immunologic testing should be obtained at the time of any suspected rejection episode(s).

Anti-donor Antibody Determination:

Anti-donor antibody testing will be performed at baseline, and at Weeks 4, 12, and 24

All samples should be taken prior to beginning infusion of belatacept. Additionally, a sample for anti-donor antibodies (pre-dose) should be obtained at the time of any suspected rejection episode(s).

#### Pregnancy Tests:

A serum pregnancy test (minimum sensitivity 25 IU/L of ß-HCG) must be performed at a local laboratory for all WOCBP within 72 hours prior to the first dose of study medication (baseline or Day 1). Additional testing will occur at weeks 12 and 24, and week 48 for those continuing in the study.

If a female subject becomes pregnant, she will be discontinued from the study.

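### Pregnancy tests are required every 3 months throughout participation, but the visit schedule leaves 24 weeks without one in the optional extension

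*Combined protocol and SAP*

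**What the plan says.** Two places set an interval. Section 5.1 (inclusion criterion 5) asks for a negative serum test "within 72 hours prior to the start of study medication then every 3 months during the period of study participation". Section 9.7, under the timing of pregnancy testing, repeats the interval: "Every 3 months during period of study participation". That list also calls for a test at screening and "Whenever pregnancy is suspected". Neither section limits the interval to the first six months.

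Two places list weeks. Section 7.3.4 requires a test before the first dose and continues: "Additional testing will occur at weeks 12 and 24, and week 48 for those continuing in the study". Section 7.2.4, item h, agrees: "WOCBP will undergo pregnancy testing at weeks 12 and 24 as well as week 48 for those continuing in the study".

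The procedures table in section 7.1 has four marks in its pregnancy row, the last in the column reserved for patients who extend. Its column headings are damaged in the text available here, so this point relies on the prose of 7.2.4 and 7.3.4.

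Section 3.1.1 makes the second six months of belatacept optional, at the patient's preference.

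**The concern.** The extension is part of the study. Section 3.1.1 describes it as an extension of study duration with further belatacept, and sections 7.2.4 and 7.3.4 refer to women who stay in the study. The 3-month interval in 5.1 and 9.7 therefore runs through weeks 24 to 48, and the schedule in section 7 does not deliver it.

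Coordinators work from the visit schedule. Following section 7 as written would omit a safety test that 5.1 and 9.7 require, with nothing in section 7 to alert staff.

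The protocol's actions on pregnancy begin only once it is known: the provisions on study therapy in 6.2.4 and 7.3.2, the 24-hour report to the manufacturer in 9.2 and 9.7, and the discussion of fetal hazard from mycophenolate in 7.3.2. Continuing women are receiving both belatacept and mycophenolate, so a later test can mean longer exposure before any of these steps starts.

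**Working it through.** **Inputs**

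- Scheduled tests (7.2.4, 7.3.4): within 72 hours before the first dose (taken as week 0), then weeks 12 and 24, and week 48 for those who extend.
- Required interval (5.1, 9.7): 3 months.
- Visit windows (7.2.6): ±3 days from week 4 to month 6, and ±7 days at month 12. Section 7.2.6 introduces them for infusion-only visits; applying them to the testing visits is an assumption.

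**Length of 3 months**

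- Calendar: 3 × 365.25 / 12 / 7 = 13.04 weeks (91.3 days).
- Protocol convention: month 3 is week 12 (compare 3.1.3 with 4.1), so 12 weeks (84 days).

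**Gaps between scheduled tests**

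| Interval | Gap | Ratio to 13.04 weeks | Ratio to 12 weeks |
|---|---|---|---|
| Week 0 to 12 | 12 weeks | 0.92 | 1.0 |
| Week 12 to 24 | 12 weeks | 0.92 | 1.0 |
| Week 24 to 48 | 24 weeks | 1.84 | 2.0 |

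The first two intervals satisfy the rule on either reading. The third satisfies it on neither.

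**Effect of the windows**

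The nominal extension gap is 24 × 7 = 168 days. Treating week 48 as the month 12 visit:

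- shortest gap: 168 − 3 − 7 = 158 days (22.6 weeks)
- longest gap: 168 + 3 + 7 = 178 days (25.4 weeks)

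Even the shortest gap is well above 91.3 days.

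**Number of tests missing**

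- 12-week interval: after week 24, tests fall due at weeks 36 and 48, which is two. The schedule lists one.
- 13.04-week interval: the next test is due by week 24 + 13.04 = 37.04. The week 48 test follows 10.96 weeks later and is in time.

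Either way, one test is missing per continuing woman.

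**Whether another provision fills the gap**

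- Infusion-only visits (7.2.3) stop at week 20, and their procedures do not include a pregnancy test.
- Standard visits (7.2.4) go from week 24 directly to week 48.
- The local laboratory row of the procedures table refers to standard-of-care testing and does not name a pregnancy test.
- Testing on suspicion (9.7) is listed alongside the 3-month test, not in place of it.
- No clause says which section prevails.

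**The case against.** The strongest reply is that the two sets of sections can both be obeyed. Neither 7.2.4 nor 7.3.4 says its weeks are the only tests, so a site that also reads 5.1 and 9.7 could add a test between weeks 24 and 48 and comply with everything. On that view the visit list is incomplete rather than contradictory. This is fair as a matter of wording. In practice, however, staff would have to notice that a specific list falls short of a general rule stated elsewhere, so the defect stands.

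The gap is also part of a wider omission. Section 1.3 describes monthly dosing and 3.1.1 provides six further months of belatacept, yet section 7 names no extension visit before week 48. That is correct, and it is a reason to repair both together.

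Other safeguards exist. Section 9.7 requires a test on suspicion and tells subjects to contact the investigator at once about a missed or late period, and 5.1 and 5.2 make contraception a condition of entry. These reduce the chance that a pregnancy goes unnoticed for the full interval. The protocol nevertheless set periodic testing in addition to them.

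Finally, the scale is small. The trial enrols 20 men and women, the extension is optional, and the documents do not say how many continuing subjects will be women of childbearing potential; there could be none. This limits the consequence but does not remove the inconsistency.

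**Conclusion.** The concern holds. Sections 5.1 and 9.7 require a test every 3 months with no exception for the extension, while 7.2.4 and 7.3.4 schedule none between weeks 24 and 48. The gap is 24 weeks, 1.84 times a calendar 3 months or 2.0 times the protocol's 12-week quarter, and one scheduled test is missing for each woman of childbearing potential who continues. The first 24 weeks are consistent with the rule.

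This rests on two readings: that the optional six months count as study participation, which the protocol's own wording supports, and that sites will schedule tests from section 7. It is a safety-procedure inconsistency with no bearing on sample size, endpoints or analysis. It should be corrected because it concerns subject safety and costs little to put right.

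**What to change.** Reconcile sections 7.2.4 and 7.3.4 and the procedures table with sections 5.1 and 9.7, so that a single stated testing interval covers weeks 24 to 48. The sponsor and investigator must decide that interval; this review does not propose one. Whatever they decide, all five places should state it in the same terms, and the visit at which any added test is taken should appear in the schedule.

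The cost is an amendment to the wording and, if the 3-month rule is kept, one local test per continuing woman of childbearing potential. With monthly dosing she should already be attending for infusions, but section 7 does not list those extension visits, so the same amendment should add them.
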